5.3.2.2.3 Infant outcomes

Minor congenital malformations

Congenital malformations will be classified according to the MACDP classification system [see Section 5.4.4.1]. Minor congenital malformations are part of the secondary objectives for this study. All potential minor congenital malformations will be evaluated by at least 3 qualified, independent teratologists using all available medical records [see Section 10].

Confidential

The classification of potential minor congenital malformations will be based upon the teratologist's adjudication, who will be blinded to patient exposure status. Adjudicated minor congenital malformations will not be included in the analysis of the primary objective. All minor congenital malformations will also be classified according to the EUROCAT classification system, if different from MACDP classification.

Size for gestational age

All live births will be classified as small, appropriate, or large for gestational age using the World Health Organization definition [WHO 1995] of birth weight below the 10th percentile, between the 10th and 90th percentile, and above the 90th percentile for age, respectively.

Low birth weight

An infant with low birth weight will be classified as weighing under 2500 g [cdc.gov_b]. Low birth weight can be subclassified into very low birth weight (< 1500 g) and moderately low birth weight (1500 g to 2499 g).

Infant death

An infant death refers to the death of a live-born infant within the first year of life. Infant deaths will be subclassified as neonatal deaths (≤ 28 days of life) and infant deaths (29 to 365 days of life).

Hospitalization for serious illness

Hospitalizations for serious illness refer to in-patient admissions for treatment of potentially life threatening illnesses among live-born infants within the first year of life. Serious illnesses will be based on HCP-reported diagnosis.

Postnatal growth and development

Domains of developmental milestones (i.e., social/emotional, language/communication, neurocognitive, movement/physical development milestones) by age will be defined by guidelines provided by the CDC [CDC 2019]. As recommended by the CDC, the World Health Organization Growth Charts (suitable for use in the US and EEA from birth to 24 months) will be applied for this study, where infant growth measurements will be used to estimate gender-specific weight-for-length, head circumference-for-age, length-for-age, and weight-for-age percentiles. Other growth charts may be utilized as appropriate (e.g., Fenton Preterm Growth Chart for preterm infants) [Fenton 2013]. Developmental milestones will be collected as part of routine clinical practice with pediatrician-determined results of infant stats (i.e., below, above, or at age-appropriate achievement) in each of the domains listed above. 'Ages and Stages' or similar standardized assessments may be collected for this study if performed as part of routine clinical care – no additional information will be mandated for collection as part of this study.

Doc No D-23.335

5.3.3 Covariate definition and measures

5.3.3.1 Baseline covariates

- Patient demographics and characteristics
 - Age of patient (mother) at the time of enrollment.
 - Education level (doctoral or professional degree, master's degree, bachelor's degree, associate degree, postsecondary nondegree award, some college, no degree, high school diploma or equivalent, no formal education credential).
 - Race (American Indian or Alaska Native, Asian, Black or African American, Hawaiian or Other Pacific Islander, White, Other/Unspecified).
 - Ethnicity (Hispanic or Latino and Not Hispanic or Latino) if permitted by local regulations.
 - Height (cm or in).
 - Weight (kg or lbs.); pre-pregnancy and current weight.
 - BMI (derived from height and current weight).
- Paternal demographics and characteristics
 - Height (cm or in).
 - Weight (kg or lbs).
 - BMI (derived from height and current weight).
- Lifestyle risk factors (before and during current pregnancy)
 - Smoking (current, former, never).
 - Caffeine consumption (Y/N).
 - Alcohol use (Y/N, if Y, number of drinks per week).
 - Illicit drug use (Y/N).
 - Marijuana use (Y/N).
- Current pregnancy information (calendar provided to help recall)
 - Date of the LMP.
 - Date of conception.
 - Gestational age at time of enrollment visit.
 - Estimated delivery date.
 - Date and results of any prenatal tests.
 - Pregnancy complications: physician reported preeclampsia, pregnancy-induced hypertension, preterm labor, gestational diabetes, placenta previa.
 - Pregnancy history.
 - o Parity: number of pregnancies carried to a variable gestational age (> 20 weeks).
 - o Gravidity: number of pregnancies.
 - o Previous preterm birth [for definition, see Section 5.3.2.2.2].
 - o Previous spontaneous abortions [for definition, see Section 5.3.2.2.2].

- Previous elective or therapeutic terminations [for definition, see Section 5.3.2.2.2].
- o Reason for any elective or therapeutic termination.
- o History of congenital malformations.
- o Other (specify).
- Surgical and medical history or significant maternal medical conditions other than insomnia.
- Insomnia history including but not limited to insomnia diagnosis date and duration of insomnia disorder.
- Family reproductive history including:
 - Multiple births.
 - Pregnancy complications (i.e., preeclampsia, pregnancy-induced hypertension, preterm labor, gestational diabetes, placenta previa).
 - Congenital malformations.
 - Spontaneous abortions.
 - Preterm births.
 - Chromosomal anomalies.
 - Evidence of developmental delays.
- QUVIVIQ treatment: start and stop dates, dose, dosing frequency, reason for discontinuation, if applicable.
- Current and prior medication use starting at 3 months prior to conception (including all prescription and any other over-the-counter treatments, other insomnia treatments, folic acid and other vitamins, herbal remedies or supplements, vaccinations, or other medications used to treat chronic conditions or comorbidities): start and stop dates, if applicable.
- Safety events that occurred from the date of the LMP to study enrollment: patient AEs
 and SAEs in Cohort A (following QUVIVIQ exposure) and in Cohort B including
 event, start date, ongoing or end date, seriousness, severity, relationship to QUVIVIQ,
 outcome, and action taken.

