5.2 Study population

Women with insomnia disorder in a standard-of-care setting, and pregnant at time of enrollment, will be prospectively enrolled prior to any pregnancy outcome. Women with insomnia disorder exposed to QUVIVIQ at any time during pregnancy or within 5 half-lives prior to conception will be assigned to Cohort A. Women with insomnia disorder who have been exposed to non-ORA medications for insomnia during pregnancy or within 5 half-lives of the respective insomnia medication prior to conception (Cohort B1) and women with insomnia who have not been exposed to any insomnia medication during pregnancy and within 5 half-lives of any insomnia medication taken prior to conception (Cohort B2) will comprise the comparator group (Cohort B).

Secondary data sources will be used to evaluate the rate of complications in parallel with external comparator cohort(s) representing the prevalence of birth defects in the general population [see Section 5.4.4]. To reduce bias that may occur if outcome information is known prior to enrollment, pregnant women should be enrolled in the study as soon as their pregnancy is known, prior to any informative prenatal testing (such as maternal serum screening or amniocentesis) where the knowledge of the primary study outcome of their pregnancy would be known – either normal or abnormal), and preferably in the first trimester before 20 weeks gestation.

Women who were exposed to QUVIVIQ during pregnancy or within 5 half-lives prior to conception, but for whom the outcome of pregnancy is known prior to enrollment (retrospective pregnancies), will be enrolled in this study and analyzed in a separate case series.

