5.2.1.1 Eligibility criteria for prospective pregnancies

Inclusion criteria

- Diagnosis of insomnia disorder prior to pregnancy.
- Pregnancy is ongoing and outcome of pregnancy (i.e., pregnancy loss or live birth) is not known.
- One of the following:
 - Woman exposed to QUVIVIQ at any time during the current pregnancy or within 5 half-lives prior to conception.
 - Woman exposed to other, non-ORA medications for insomnia during pregnancy or within 5 half-lives of the respective insomnia medication prior to conception.

Confidential

- Woman unexposed to any insomnia medication during pregnancy and within
 5 half-lives of any insomnia medication taken prior to conception.
- Able and willing to consent to the conditions and requirements of the registry. If the patient is a minor, able and willing to consent/assent according to local regulations.
- Agrees to electronically sign the Release of Medical Information Form permitting the study staff to contact her HCPs (e.g., primary care provider, insomnia specialist, psychiatrist, obstetrician, nurse midwife) and the infant's HCP (e.g., pediatrician) for medical information.

Exclusion criteria

- Exposure to any ORA other than QUVIVIQ (including BELSOMRA® (suvorexant), DAYVIGO® (lemborexant), any ORA newly approved during the study period, or any ORA in pre-market clinical studies) during the current pregnancy or within 5 half-lives of the respective medication prior to conception.
- Woman is currently participating in an interventional study or has taken an investigational product within 3 months prior to conception or during the current pregnancy.

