5.6.1.1 Baseline

The baseline information and any data up to the point of enrollment will be collected at the enrollment encounter. Baseline information will be collected to confirm patient eligibility, collect relevant medical history, and characterize the current pregnancy status of the patient. The following data elements will be collected at baseline:

General

- Identification number.
- Contact details of HCP at initial contact with the registry.
- Date of initial report.
- Documentation of informed consent/assent.
- Reporter of information (e.g., patient, HCP).
- Inclusion/exclusion criteria.

• Maternal Information

- Age of patient (mother) at conception.
- Patient demographics and characteristics: height, pre-pregnancy and current pregnancy weight, education, BMI, race, ethnicity (if permitted by local regulations).
- Medical history: genetic disorder, previous pregnancies and their outcome (parity, gravidity, previous preterm births, previous spontaneous abortions or elective or therapeutic terminations, reasons for any elective or therapeutic termination, history of congenital malformations), hypertension, diabetes, seizure disorder, autoimmune disease, lifetime history of psychiatric diseases (e.g., major depression, anxiety, psychotic diseases), known risk factors for adverse pregnancy outcomes including exposures to known teratogens [Appendix 2], history of oncologic disorders, and any previous exposure to chemotherapy and radiotherapy.

23 October 2023, page 50/90

Confidential

- Insomnia history including but not limited to the earliest insomnia diagnosis date and duration of insomnia.
- Family reproductive history (e.g., multiple births, pregnancy complications [i.e., preeclampsia, pregnancy-induced hypertension, preterm labor, gestational diabetes, placenta previa], congenital malformations, spontaneous abortions, premature births, chromosomal abnormalities, evidence of developmental delays).
- Paternal Information (to be reported by the mother)
 - Demographics and characteristics: height, weight, BMI.
- Current pregnancy
 - Date of the LMP.
 - Ultrasound results for gestational dating.
 - Prenatal test results (e.g., rubella titer, toxoplasmosis, venereal disease research laboratory test, hepatitis screen, ultrasounds, amniocentesis, maternal serum alpha-fetoprotein screen, glucose screen).
 - Number of fetuses.
 - Complications during pregnancy (including any adverse drug reaction).

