5.7.4 Analysis sets and groups

5.7.4.1 Baseline descriptive analysis

Patient characteristics are described in Section 5.7.2.1.

Patient disposition characteristics, including summaries for enrolled patients, patients in the analysis set, completers and early withdrawals with the reasons for early discontinuation will be provided. In addition, demographic information (e.g., age, race/ethnicity, BMI), clinical characteristics, including comorbidities and medications, other potential factors that may affect pregnancy outcome, and QUVIVIQ exposure will be described.

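### Maternal baseline BMI is defined on current weight at enrollment although pre-pregnancy weight is collected, so it carries gestational weight gain into the baseline comparison of the cohorts

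*Protocol*

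**What the plan says.** Under maternal characteristics, Protocol Section 5.3.3.1 lists "Weight (kg or lbs.); pre-pregnancy and current weight" and then defines "BMI (derived from height and current weight"). The same definition is used for the father, where only one weight is listed and it does no harm.

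No other section gives maternal BMI a different basis. Section 5.6.1.1 lists "height, pre-pregnancy and current pregnancy weight, education, BMI, race, ethnicity" without saying which weight enters the BMI, and Appendix 1 lists the two weights again. These places neither repeat nor correct the definition, so the point rests on one line of Section 5.3.3.1.

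On timing, Section 5.6.1.1 states: "The baseline information and any data up to the point of enrollment will be collected at the enrollment encounter". Eligibility (Section 5.2.1.1) asks only that "Pregnancy is ongoing and outcome of pregnancy (i.e., pregnancy loss or live birth) is not known". Section 5.2 wants enrollment "preferably in the first trimester before 20 weeks gestation", which is a preference and not a limit.

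On use, Section 5.7.4.1 names BMI for the baseline description: "demographic information (e.g., age, race/ethnicity, BMI").

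**The concern.** In a pregnancy registry, a baseline BMI is meant to describe the mother's body size before the pregnancy could alter it. Weight at enrollment does not do that. It rises with gestational age, so the derived BMI is partly a measure of when the woman joined.

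It is also measured after exposure has begun for many women. Entry to Cohort A or B1 requires exposure to an insomnia medication, and Section 5.7.2.1 ends the first trimester at 13 weeks and 6 days. For a woman enrolled later than that, current weight is taken wholly after the exposure window of the primary analysis.

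What is at stake is the baseline comparison. The cohorts are not randomized, and Section 5.9.1.4 relies on examining covariate distributions between Cohorts A and B to judge confounding. A BMI row that moves with enrollment week is a poor guide for that purpose.

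**Working it through.** The protocol states no figure for this covariate, so there is nothing to reproduce. The check has two parts: whether enrollment week can vary enough to matter, and how far the definition moves BMI.

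**1. Can enrollment week vary?** Yes, on the protocol's own terms.
- Sections 5.2 and 5.2.1.1: enrollment before 20 weeks is preferred, but any ongoing pregnancy with unknown outcome qualifies.
- Section 5.4.2: the contact schedule is adapted to gestational age at enrollment.
- Section 5.7.1.3 and Table 5: the 18–20-week ultrasound is among the tests that decide inclusion, and women with normal results known before enrollment stay in the primary analysis.
- Table 6: a sensitivity analysis of spontaneous abortion by gestational age at enrollment is planned.

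**2. How far does BMI move?** Let W be pre-pregnancy weight (kg), G the gain by enrollment (kg) and h height (m).
- BMI as defined = (W + G) / h²
- Pre-pregnancy BMI = W / h²
- Shift = G / h²

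Height, weight and gain are all assumptions, because the protocol gives none of them.

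At h = 1.65 m, h² = 2.7225:

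| Assumed gain G | Shift G / 2.7225 | BMI as defined for W = 65 kg |
|---|---|---|
| 0 kg | 0 | 23.9 |
| 1 kg | 0.37 | 24.2 |
| 5 kg | 1.84 | 25.7 |
| 8 kg | 2.94 | 26.8 |
| 12 kg | 4.41 | 28.3 |

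Range over assumed heights:
- h = 1.55 m (h² = 2.4025): 1 kg adds 0.42 and 12 kg adds 4.99 kg/m2.
- h = 1.75 m (h² = 3.0625): 1 kg adds 0.33 and 12 kg adds 3.92 kg/m2.

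So the same woman has a recorded baseline BMI about 4 kg/m2 higher after a 12 kg gain than after a 1 kg gain (28.3 − 24.2 = 4.1), with no difference in pre-pregnancy body size.

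**3. From one woman to the cohort comparison.** At a common height, the artificial difference in mean BMI between two cohorts is (mean gain in A − mean gain in B) / h². At 1.65 m, each 1 kg difference in mean gain by enrollment produces about 0.37 kg/m2. It is zero if both cohorts have gained the same on average by enrollment. The protocol gives no basis for estimating this difference.

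**4. After the change.** With BMI taken from W / h², the gain component is zero by construction.

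**The case against.** The strongest reply is that BMI has no stated inferential role. It is absent from the key adjustment covariates in Section 5.7.4.3 (maternal age, earlier terminations, other insomnia treatment, and alcohol, smoking, marijuana and drug use). It is also absent from the subgroups in Sections 5.7.2.1 and 5.7.4.4, from the standardization variables for the external comparison and from the example confounders in Section 5.9.1.4. Covariate adjustment is itself only something that may be explored. All of this stands. A reader might infer that the definition biases the malformation comparison, or the results for preeclampsia, gestational diabetes and size at birth. The protocol does not support that, because it names no analysis in which BMI enters those estimates. What remains is that the choice of further covariates is left partly open, so the variable could be picked later.

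A second reply is that no information is lost: height, both weights and gestational age at enrollment are all recorded, so pre-pregnancy BMI can be computed at any time. This is true and makes the fix cheap. But the protocol fixes which BMI is the covariate, and the baseline table would follow that definition.

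A third reply is that Sections 5.2 and 5.4.5 press for early enrollment, that Cohort B follows the same procedures (Section 5.1), and that it is recruited where feasible from the same centers (Section 5.9.2). This makes large gains before enrollment less typical and gives no positive reason to expect the cohorts to differ in enrollment week. The distortion of the comparison is therefore possible, not shown.

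A reader might also infer that BMI ought to join the adjustment list. That is a separate proposal and does not follow from a faulty definition.

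**Conclusion.** The point holds as a defect in the definition of one baseline covariate. The protocol has the suitable input and specifies the other one. For an individual woman the shift is about 0.4 to 4.4 kg/m2 at 1.65 m for gains of 1 to 12 kg, or 0.3 to 5.0 kg/m2 over heights of 1.55 to 1.75 m, all on assumed values. For the comparison of Cohorts A and B, the effect depends on a difference in mean gain by enrollment that cannot be estimated from the protocol and may be small.

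The reach is limited to the BMI row of the baseline tables and to any exploratory adjustment that might later use this variable. The non-inferiority test, its margin, the sample size and the named adjustment covariates do not depend on it. It is worth correcting because it changes a reported result and the remedy is simple, not because it threatens the primary conclusion.

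**What to change.** In Section 5.3.3.1, define maternal BMI as derived from height and pre-pregnancy weight. Where pre-pregnancy weight is missing, allow the earliest recorded first-trimester weight and flag those women. State the same basis where BMI is listed in Section 5.6.1.1, and use this BMI in the tables described in Section 5.7.4.1. Report current weight as its own row, next to gestational age at enrollment. The paternal definition can stay.

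The cost is a short change of wording. Height, both weights and gestational age at enrollment are already baseline items, so the main definition needs no new data. The drawback is that pre-pregnancy weight may be self-reported or missing for some women. Showing how many values come from the fallback in each cohort lets a reader judge how much that matters.

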5.3.3.2 Covariates during follow-up

Covariates to be collected during pregnancy, at delivery, during infant follow-up, and at early termination of study participation (if applicable) are described in Section 5.6.1.

Confidential

5.3.4 Validity and reliability

Data will be collected from the patient's and infant's HCPs or directly from the patient and entered into the eCRF by trained CC research staff [see Section 5.4.2]. Standard definitions for the classification of pregnancy outcomes have been used and proper citations have been provided, where applicable. Some outcomes, such as pregnancy complications, will rely on the report of a diagnosis (e.g., hypertension) and not individual measurements (e.g., systolic and diastolic blood pressure values). Reliability of the data is subject to what is reported by the HCP and/or patient, and methods to ensure the quality of the data to the greatest extent possible are provided in Section 5.6.2. Published literature can be used for comparison of the distribution and/or frequencies of key covariates.

The primary outcome of major congenital malformations and the secondary outcome of minor congenital malformations will be defined using the standard classifications provided by MACDP and EUROCAT, with an independent review by the Adjudication Committee of teratologists who will be blinded to the patient's exposure status [see Section 10].

5.4 Data sources

5.4.1 Collection of data on the electronic case report form

Patient data are obtained from the patients and their HCPs. The degree of detail and completeness of data collected is dependent on local clinical practice.

5.4.2 Data collection during the observation period

The CC is responsible for overseeing patient enrollment (i.e., determining eligibility and obtaining informed consent and permission for medical form release either over the phone or through the app associated with the website) and all patient and HCP contacts.

After a patient provides consent, the CC research staff will obtain demographic and contact information in addition to baseline information at the time of enrollment. All patient and HCP contact information will be confidential and will remain at the CC. Women with retrospective pregnancies will provide retrospective information on exposures and events during the QUVIVIQ-exposed pregnancy. For pregnancies followed prospectively, and when applicable among retrospective pregnancies, infant HCP contact information will be obtained at the delivery follow-up (estimated within 4 weeks of delivery date). The CC research staff will contact the patient each trimester to ascertain the occurrence of pregnancy outcomes or other events [see Section 5.3.3 for list of variables]. Data collection schedules will be modified as necessary based on the gestational age at enrollment. When permitted by local regulations, patients will also have the option to directly enter data into the eCRF through the website-associated app. All variables collected through the app will be the same as those collected by the CC. Regardless of how the data is collected, all time points for data collection will be the same. Below is a list of expected contact points for data collection with patients and HCPs.

Confidential

Expected contact with patient (actual contact will depend on the gestational age at enrollment):

- Enrollment.
- End of trimester 1 (approximately 14 gestational weeks).
- Mid-trimester 2 (approximately 21 gestational weeks).
- Mid-trimester 3 (approximately 34 gestational weeks).
- Estimated delivery date plus 4 weeks.
- Birth plus approximately 12 weeks, 26 weeks, and 52 weeks (for live births only).

Expected contact with the patient's HCP:

- Enrollment.
- Mid-trimester 2 (approximately 21 gestational weeks).
- Estimated delivery date plus 4 weeks.

Expected contact with the infant's HCP (live births only):

- Estimated delivery date plus 4 weeks.
- Birth plus 12 weeks.
- Birth plus 26 weeks.
- Birth plus 52 weeks.

After enrollment, for each expected contact time, there will be at least 3 attempts made to contact the patient and/or the HCP via phone, email, fax, and app-based notifications as appropriate, approximately 10 business days apart. If data is obtained after a follow-up interval has passed, the CC research staff will accept and enter the data and continue follow-up of the patient.

If the patient experiences an adverse pregnancy outcome or has an elective or therapeutic termination or a termination of unknown cause, the HCP and the patient will be encouraged to report the outcome to the CC research staff as soon as possible. In the event of an elective or therapeutic termination, spontaneous abortion, fetal death or stillbirth, communication with the patient will cease after pregnancy outcome information has been obtained. Idorsia Drug Safety Department will follow-up on all SAEs, including information about fetal or maternal death, with the patient's HCP.

